3.3.3 Exploratory outcomes

- Length of hospital stay (days) at 90 days
- Discharge destination (remains in hospital, home, care home) at 90 days
- Number of antibiotics doses received during first 7 days after randomisation
- Highest recorded CRP concentration (mg/L) during first 7 days after randomisation
- Highest recorded WBC count (x10⁹/l) during first 7 days after randomisation
- Highest recorded respiratory rate (RR)/minute during first 7 days after randomisation
- Highest recorded temperature °C during first 7 days after randomisation
- Highest recorded NEWS-2 score during first 7 days after randomisation
- Lowest recorded lowest oxygen saturations (%) during first 7 days after randomisation
- Caregiver quality of life (EQ-5D-5L)

4 TRIAL DESIGN

CLASP is a prospective randomised open-label blinded-endpoint (PROBE) phase 3 trial.

- Population: Hospitalised adult patients within 14 days of admission for acute stroke when starting (or within 24 hours of starting) non-macrolide antibiotics for PSP.
- Intervention: Addition of clarithromycin 500mg bd (route of administration will be determined by local clinical team based on clinical condition and availability of route of administration in line with local IVOS policy) for 5 days in addition to usual non-macrolide antibiotic therapy.
- Comparator: Local guideline usual antibiotic therapy for PSP where macrolides are not indicated.
- Outcome: Primary outcome is blinded mRS score at 90 days.
- Time: Individual data will be collected over 90 days.

The CLASP study will include an 18-month internal pilot phase to confirm feasibility. During this phase, a target of 36 sites (80% of total sites) and 246 participants (21% of the total sample) at a rate of 0.55-0.7 participants/site/month during the first 6 months and 0.76 participants/site/month for the remaining 12 months will be set* (this will only apply to sites that have been opened for 3 months or more). Following the internal pilot phase, progression to the main recruitment phase will be based on a stop-go decision for both site and participant internal pilot targets (Table 2):

| Progression criteria | Red | Amber | Green |
|--|-------|-----------|-------|
| % threshold | <75% | 75-99% | ≥100% |
| Number of sites open | <27 | 27-35 | ≥36 |
| Recruitment/site/month | <0.54 | 0.54-0.71 | 0.72 |
| Total number of participants recruited | <185 | 185-245 | ≥246 |
| Proportion with primary outcome* | <80% | 80-90% | >90% |

Table 2: Internal pilot progression criteria

*Where the denominator is the number who have reached the 90-day period, undergone survival check and been contacted the maximum number of times in accordance with the trial protocol

The progression criteria and actions are as follows:

- Green: ≥100%: continue seamlessly to main recruitment phase
- Amber: 75-99%: Discuss feasibility and develop improvement plan with the Trial Steering Committee (TSC) to present to Funder
- Red: <75%: Discuss closure options with the TSC and Funder

If there is inconsistency in the scoring of the progression criteria, then overall the trial will be categorised according to the criterion that is furthest from achieving the progression threshold (e.g. if four criteria are green but one is amber, the trial will be categorised as amber).

If criteria are met for progression, the main recruitment phase (27 months) will recruit the remaining additional 9 sites (during the first 6 months) and 920 participants. The trial will aim for a recruitment rate of 0.7 participants/site/month for the additional 9 sites during set-up and 0.8 participants/site/month otherwise.

5 TRIAL SETTING

CLASP is a multicentre trial and will take place across at least 45 NHS hyperacute and acute stroke units in the UK.

Sites will be identified through SSNAP/Scottish Stroke Care Audit, NIHR CRN, Northern Ireland Stroke Research Network, Welsh Stroke Research Network, Scottish Stroke Research Network and BIASP.

6 PARTICIPANT ELIGIBILITY CRITERIA

6.1 Inclusion criteria

- Age ≥18 years
- Acute stroke (ischaemic stroke or intracerebral haemorrhage [ICH]) within the past 14 days
- Starting (or within 24 hours of starting) non-macrolide antibiotics for a new diagnosis of PSP*
- Written informed consent from participant or from next of kin/designated representative or consultee or independent physician if participant lacks capacity (by phone if required)
- Women of childbearing potential must have a negative highly sensitive serum (beta-human chorionic gonadotropin [beta-hCG]) or urine test at screening (see Appendix 1 for further information)

*In the CLASP trial, PSP is defined as a clinician diagnosis of pneumonia within 14 days of stroke onset with or without supporting radiographic evidence. Participants can be included after nonmacrolide antibiotics have been started for PSP provided they are randomised within 24 hours of the first dose. Clinical data will be collected to enable classification as probable or definite post-stroke pneumonia using published criteria [2].

Non-macrolide antibiotic use for disorders other than pneumonia is allowed at the point of randomisation.

6.2 Exclusion criteria

- Requirement for macrolide therapy as usual care
- Confirmed respiratory viral infection (e.g. COVID-19, influenza) at point of screening*
- Known antibiotic treatment for chest infection or pneumonia within the last two weeks (single doses or less than 3 days of treatment is allowed)
- Known toxin positive *C.difficile* infection in the past 12 weeks
- Contraindications or major cautions to macrolide antibiotic use:
 - Known hypersensitivity to clarithromycin, its excipients or other macrolide antibiotics
 - Established diagnosis of myasthenia gravis
 - Diagnosis of long QT syndrome
 - QTc interval >460ms on last ECG before screening[†][36]
 - Known hypokalaemia (K+ < 3.5 mmol/l) which has not been corrected

- Known hypomagnesaemia (Mg2+ < 0.70 mmol/l) which has not been corrected
- History of ventricular tachycardia
- History of cardiac arrest
- Severe hepatic impairment defined as AST, ALT or bilirubin > 3 times ULN or known diagnosis of cirrhosis
- Current use of medicine(s) known to increase risk of QT prolongation that in the opinion of the investigator cannot reasonably be withheld for the duration of study treatment plus 3 days (see Appendix 2)
- Current use of medicine(s) that are contra-indicated in combination with clarithromycin that in the opinion of the investigator cannot reasonably be withheld for the duration of study treatment plus 3 days (see Appendix 2)
- Women of childbearing potential who are pregnant, breastfeeding or who are unwilling to use appropriate contraception or abstain from sexual intercourse for 3 days (72 hours) after the last dose of clarithromycin (see Appendix 1 for definitions and information on acceptable methods of contraception)
- Plan for imminent mechanical ventilation
- End-of-life care
- Previously randomised into the CLASP study

* A test for viral infection is not required by protocol, this is only if it is done for routine clinical care.

[†]Some ECG machines may provide different measures of QTc. For trial eligibility, the longer result should be used.

Co-enrolment in other Clinical Trial of Investigational Medicinal Products (CTIMPs) is not permitted while participating in CLASP. Co-enrolment in observational studies, diagnostic studies or other research may be permitted subject to agreement of the Sponsors and Chief Investigators of both studies.

6.3 Caregiver eligibility

Caregivers completing burden and quality of life assessments will be aged 18 years or older and providing unpaid support to patients who are living in a private residence.

The main caregiver will be identified by the participant or next of kin but must be the person deemed most likely to be providing informal care to the participating patient.

7 TRIAL PROCEDURES

7.1 Recruitment

7.1.1 Participant identification

Potential participants will be identified by case note review by a member of the clinical team or by their attending doctor whilst in-patient in a stroke unit.

Eligibility will be confirmed by a medically qualified investigator.

7.1.2 Screening

Patients will be screened to determine if the following conditions are met:

- 1. Adult with acute stroke
- 2. Within 14 days of admission

- 3. Starting (or within 24 hours of starting) non-macrolide antibiotics according to local stroke unit policy
- 4. No other reason for exclusion

No additional procedures are required for screening.

7.1.3 Payment

There will be no payment to participants for participation.

7.2 Consent

7.2.1 Participant consent

Following identification of a potential participant by the clinical team and screening, potential participants will be approached in person and asked whether they would consider taking part in the trial. If the person approached lacks capacity, designated (e.g. relative) or professional (independent physician) consultees will be approached to discuss their participation. Consent may be obtained via telephone from a designated or professional consultee where no consultee is available in person. Participants or their representatives may decline to participate for any reason without explanation.

Those who are willing to hear more will be given a Participant Information Sheet (PIS) and a time will be arranged for further discussion with a member of the research team. Participants or their representatives will be permitted to consent at the initial visit, without 24-hour delay, as the population being studied will require the trial antibiotic treatment to start as quickly as possible upon diagnosis of PSP to maximise chances of success.

Potential participants or their representatives will be given an opportunity to ask any questions and those who wish to participate will be asked to sign an Informed Consent Form (ICF). Two copies will be signed (one each for the participant and the site file) and a copy of the signed consent form will be inserted into the patient's record. If a person has capacity to consent but is unable to write due to physical disability, an independent witness' signature will be used to confirm consent.

Consent will be taken by one of the designated investigators or by a delegated study research nurse (in which case it will be countersigned by an investigator).

Participants are free to withdraw consent for any aspect of the trial at any time and for any reason. They will be provided with contact details for local research staff via the PIS, which can be used should they wish to discontinue with the trial after discharge. If the participant wishes to withdraw from the study treatment, the reason(s) will be sought (but do not need to be given), and permission will be sought to continue with follow-up. If the participant wishes to withdraw from all study participation, the reason(s) will be sought (but do not need to be given). Unless the participant actively states that existing data, and/or future data from medical records may not be used, data will be used in accordance with the original signed ICF.

Participants who were consented by a representative and who are found to have regained capacity during the trial will be given a PIS outlining what their enrolment into the trial has entailed and, if they wish to continue in the trial, will be asked to complete an ICF to be stored in the participant's record and site file. If the participant has been discharged from hospital at the point capacity is regained, telephone or online re-consent is acceptable. If they do not consent to continuing in the study, they will be withdrawn. In this scenario, they will be asked to consent to use of their data. If this is not given, all of their data will be deleted.

A summary of who can give consent for the trial is shown in table below.

| Summary hierarchy of informed consent for an incapacitated adult | | |
|--|---|--|
| England, Wales and Northern Ireland | Scotland | |
| Personal legal representative / consultee | Personal legal representative. | |
| A person not connected with the conduct of the trial who is (a) suitable to act as the legal representative by virtue of their relationship with the adult, and (b) available and willing to do so. Professional legal representative. | 1A. Any guardian or welfare attorney who has power to consent the adult's participation in research. | |
| | 1B. If there is no such person, the adult's nearest relative as defined in section 87(1) of the Adults with Incapacity (Scotland) Act 2000. | |
| | Professional legal representative. | |

Table 3: Summary hierarchy of informed consent for an incapacitated adult

7.2.2 Additional consent provisions for collection and use of participant data

Participants will be invited to consent for longer-term follow-up (funding sought separately) via record linkage to routinely-collected healthcare data (e.g. 6-month mRS, recurrent stroke, recurrent PSP from the SSNAP registry/HES, longer-term survival (ONS) and dementia status).

7.2.3 Caregiver consent

Caregivers completing burden and quality of life assessments will be identified at the point of consent. Their eligibility will be checked (see section 6.3) and if suitable, they will be provided with a Caregiver Information Sheet and the opportunity to ask any questions. Those who wish to participate will be asked to sign a Caregiver Consent Form.

If consent is being given by a professional legal representative because a caregiver or other representative is not available, consent will only be obtained to approach a caregiver if and when a caregiver or other representative is identified.

Caregivers are free to withdraw from participating at any time for any reason. Unless the caregiver actively states that existing data may not be used, data will be used in accordance with the original signed Consent Form.

7.3 Randomisation

Patients will be randomised 1:1 to the following drug regimens:

- Intervention arm: Clarithromycin 500mg twice daily for 5 days total (route of administration will be determined by the local clinical team based on clinical condition and availability of route of administration in line with local IVOS policy) in addition to usual non-macrolide antibiotic treatment.
- Usual care: Local stroke unit usual non-macrolide antibiotic treatment.

A mixed minimisation/randomisation method designed to maintain balance with respect to baseline age (<80 v \geq 80 years), stroke severity (National Institutes of Health Stroke Scale (NIHSS) score <12 v \geq 12) and trial centre will be applied.

The randomisation list, the program that generated it and the random seed used will be stored in a secure network located within the Robertson Centre for Biostatistics (RCB), accessible only to those responsible for provision of the randomisation system.

CLASP

7.3.1 Method of implementing the randomisation/allocation sequence

Consented participants that fulfil all screening criteria will be allocated to either the treatment arm or usual care in a 1:1 ratio, via a web-based interface integrated into the electronic Case Report Form (eCRF) designed and managed by RCB.

Investigators will be informed of the treatment arm allocation in the eCRF and will prescribe clarithromycin as appropriate.

7.4 Blinding

CLASP is an open-label study with no blinding of treatment to participants or care providers. Primary outcome assessors will be independent of the clinical research team, blinded to treatment and will not have access to patient records.

7.5 Baseline data

Baseline information will be collected from consented participants that meet all eligibility criteria. This includes but is not limited to:

- Baseline demographics:
 - Date of birth
 - Sex
 - Ethnicity
 - Pre-stroke mRS
 - Baseline EQ-5D-5L
- Time since symptom onset or last seen well to admission and randomisation
- Vascular risk factors:
 - Hypertension
 - Smoking history
 - Alcohol intake
 - Atrial fibrillation
 - Diabetes
 - Dyslipidaemia
 - Coronary artery disease
 - Peripheral vascular disease
 - Previous stroke
- Selected past medical history:
 - Chronic lung diseases
 - Cancer
 - Dementia
 - Medications at baseline
- Stroke subtype:
 - Acute ischaemic stroke
 - Intracerebral haemorrhage
- Baseline stroke severity at admission (NIHSS score)
- Thrombolysis and/or thrombectomy treatment
- Current nutritional status:
 - Nil by mouth
 - Normal diet and fluids
 - Modified diet and fluids
 - Nasogastric tube feeding
 - Peripheral parenteral nutrition
- Previous treated infection earlier in this admission and/or 6 weeks prior to enrolment

CLASP

- Highest recorded in the 72 hours preceding randomisation:
 - Plasma CRP concentration (mg/L)
 - White blood cell (WBC) count and neutrophil count
 - RR (/minute)
 - Temperature (°C)
 - NEWS-2 score
- Lowest oxygen saturations (%)
- Oxygen requirements
- Presence of unilateral or bilateral chest signs on examination
- Clinical chest X-ray (CXR) or other radiology findings
- Antibiotic treatment since admission including initial antibiotic treatment plan
- Health and social care resource use
- Caregiver quality of life (EQ-5D-5L)

7.6 Follow-up assessments

The trial will comprise of 4 visits: Screening, Randomisation, Day 7 and Day 90 follow-up.

The Day 7 (+3) visit will be carried out by research staff who will collect information such as the following from case notes:

- Information on safety outcomes including *C.difficile* infection, and occurrence of defined SAEs (see section 9)
- Clarithromycin dose, doses administered and route(s) of administration (including reasons for any non-administered doses)
- Other antibiotics and doses received
- Highest CRP concentration (mg/L) to Day 7 (+3) visit
- Highest WBC count and neutrophil count (x10⁹/l) to Day 7 (+3) visit
- Highest RR (/minute) to Day 7 (+3) visit
- Highest temperature (°C) recorded to Day 7 (+3) visit
- Highest NEWS-2 score to Day 7 (+3) visit
- Lowest oxygen saturations (%) to Day 7 (+3) visit
- Oxygen requirements
- Presence of unilateral or bilateral chest signs on examination
- Findings from clinical CXR or other chest radiology
- Contact details for follow-up (participant, consented caregiver, GP)

Participants and their caregivers/GP can be contacted by telephone, email or post between 1 week and 1 month prior to the due date of the Day 90 visit to confirm contact details and ongoing participation.

The Day 90 visit will involve local data collection by the research team and a centralised assessment (+/-7 for local research staff follow-up, +/-14 for central follow-up) by video or telephone.

Local research staff will collect the following data from the medical record at Day 90 (+/-7):

- Length of hospital stay (days)
- Mortality
- Discharge destination (remains in hospital, home, care home)
- Urgent or unplanned re-admissions
- Recurrent stroke or other vascular events

The centralised assessment will then be undertaken by appropriately trained University of Manchester staff blinded to treatment allocation. This will take place via video or telephone assessment after local research staff have carried out the mortality check. They will collect information such as the following measures:

- mRS
- Quality of Life (EQ-5D-5L)
- Stroke Impact Scale (SIS)
- Home time (number of days at usual place of residence [immediately prior to their admission] at day 90)
- Health and social care resource use (index hospitalisation and post-discharge health and social care contact up to 90 days)
- Caregiver quality of life (EQ-5D-5L)
- Zarit Caregiver Burden (ZBI-12)

The Day 90 visit marks the end of the study.

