The clinical condition of people with stroke often fluctuates during their admission. Whilst the investigator is required to maintain regular oversight, the participant's usual care team are permitted to amend clarithromycin dose and route of administration if necessary in order to meet the changing clinical needs of the participant and ensure ongoing safety. Supervision of people receiving antibiotics is a normal part of care in stroke units. Clinical staff are not required to undertake study-specific training nor are they required to be on the site delegation log as this is within the scope of their usual practice. A Clinical Information Sheet with key information including permitted dose modifications and stopping criteria is provided for insertion into the medical notes for patients randomised to the intervention arm.

In the event a participant is discharged to home or other off-site long-term care facility such as a nursing home, any remaining oral clarithromycin doses should be provided at discharge where appropriate. In the event the oral route is not available, clarithromycin must be stopped at discharge. Clarithromycin treatment must be discontinued in the event participants are transferred to another hospital or site that is not participating in the CLASP trial.

If doses are missed and ongoing treatment is not contraindicated, study drug can be continued so a total of 10 doses are given over a maximum period of seven days.

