Appendix 9 – Schedule of Procedures

| Procedure | Baseline | Day 7 (+3) | Day 90 (+/-7 for local follow-up) | Day 90 (+/-14 for central follow-up) |
|---|--------------|---------------|--------------------------------------|---|
| Screening | \checkmark | | | |
| Review eligibility | \checkmark | | | |
| Informed consent | \checkmark | | | |
| Data collection* | \checkmark | ~ | ✓ | ✓ |
| mRS | \checkmark | | | \checkmark |
| Vital signs assessment* (admission to randomisation) | ✓ | | | |
| Vital signs assessment* (randomisation to Day 5) | \checkmark | ✓ | | |
| Randomisation | \checkmark | | | |
| Start of antibiotic treatment | \checkmark | | | |
| Safety (SAEs) | | \checkmark | \checkmark | |
| Treatment compliance assessment | | ✓ | | |
| Follow-up* | | | \checkmark | \checkmark |

*See protocol sections 7.5 and 7.6 for full details

Draft version 0.6 – 10 December 2024

CLASP

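### The exploratory day-7 outcomes are defined over one window and collected over another, and the antibiotic-dose outcome does not exclude the trial drug

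*Protocol*

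**What the plan says.** The outcome definitions are in section 3.3.3, among the exploratory outcomes. Two examples are "Highest recorded CRP concentration (mg/L) during first 7 days after randomisation" and "Highest recorded NEWS-2 score during first 7 days after randomisation". White cell count, respiratory rate, temperature and lowest oxygen saturation have the same 7-day window.

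The collection instruction is in section 7.6. The matching items are "Highest CRP concentration (mg/L) to Day 7 (+3) visit" and "Highest NEWS-2 score to Day 7 (+3) visit", and the other four markers are worded alike. The items are taken from case notes by research staff. No date of the extreme value is listed.

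The schedule in Appendix 9 has a row labelled "Vital signs assessment* (randomisation to Day 5"; it is ticked at Baseline and at Day 7 (+3), and its asterisk points to sections 7.5 and 7.6 for detail.

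The antibiotic outcome in section 3.3.3 is "Number of antibiotics doses received during first 7 days after randomisation". It neither includes nor excludes clarithromycin. Section 7.6 records clarithromycin doses and other antibiotics as two separate items. Section 8.6 sets 10 clarithromycin doses over 5 days and adds that, after missed doses, "study drug can be continued so a total of 10 doses are given over a maximum period of seven days".

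**The concern.** An outcome that is the highest or lowest value in a period is only as well defined as the period. The longer the window, the more extreme the recorded value tends to be. If one participant's window is 7 days and another's is 10, their peaks are not the same quantity. If the value carries no date, the analyst cannot tell a day-3 peak from a day-9 peak and cannot recover the 7-day outcome. A later analysis plan cannot repair that, because the information would not have been captured.

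The dose count raises a separate question. Clarithromycin is an antibiotic and is given to one arm only. A count of all antibiotic doses would then differ between arms by design and would not show whether clarithromycin changed the use of other antibiotics.

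**Working it through.** **1. The windows side by side**

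| Outcome | Section 3.3.3 | Section 7.6 | Appendix 9 |
|---|---|---|---|
| CRP, white cell count | 7 days | to visit, 7 to 10 days | no window given |
| Vital signs (with NEWS-2, which is scored from them) | 7 days | to visit, 7 to 10 days | to Day 5 |

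The upper limit in 7.6 is 7 + 3 = 10 days. Sections 3.3.3 and 7.6 disagree for all six markers. The Day 5 label concerns vital signs only. By contrast, section 7.5 fixes the baseline window for these markers at the 72 hours before randomisation.

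**2. How much window length matters**

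The protocol gives no daily marker data, so this is a simulation under stated assumptions: 200,000 series of standardised daily values, first-order autoregressive with day-to-day correlation 0 to 0.8, and a daily trend of 0, -0.1 or -0.2 SD. The change in the mean maximum is given in units of the SD of the 7-day maximum.

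| Trend per day (assumed) | 10 v 7 days | 7 v 5 days |
|---|---|---|
| none | +0.23 to +0.30 | +0.20 to +0.30 |
| -0.1 SD | +0.09 to +0.12 | +0.10 to +0.17 |
| -0.2 SD | +0.03 to +0.04 | +0.05 to +0.08 |

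Window length therefore matters most if markers do not fall after entry. Participants enter within 24 hours of starting antibiotics (section 6.1), so some decline is plausible.

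**3. What this does to the comparison between arms**

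Section 7.6 applies the same rule to both arms and allocation is 1:1 (section 7.3). If visit timing has the same distribution in each arm, the expected between-arm bias is zero.

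To see what an imbalance could do, assume that 30 percentage points more clarithromycin than control visits fall on day 10 rather than day 7. This figure is an illustration; nothing in the protocol supports it.

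- No trend: 0.3 × 0.23 to 0.3 × 0.30 = 0.07 to 0.09 SD
- Trend -0.1 SD: 0.3 × 0.09 to 0.3 × 0.12 = 0.03 to 0.04 SD
- Trend -0.2 SD: 0.3 × 0.03 to 0.3 × 0.04 = about 0.01 SD

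The standard error of a difference in means with 524 per arm is √(2/524) = 0.062 SD. Even under the assumed imbalance, the shift is below one standard error when markers decline and about 1.1 to 1.5 standard errors when they do not.

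**4. The antibiotic-dose count**

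The plan's own figure reproduces: (24 h ÷ 12 h) × 5 days = 10 doses. All 10 fall within about 7 days even when dosing is extended, so a literal count adds up to 10 doses per fully treated intervention participant and none by allocation in the control arm.

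The protocol gives no SD for the dose count. Assume SDs from 5 to 20 doses and 524 per arm. At the largest, the standard error is 20 × 0.062 = 1.24 doses.

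- A built-in difference of 10: 10 ÷ 1.24 = 8.1 standard errors, power about 100%.
- A built-in difference of 5: 5 ÷ 1.24 = 4.0 standard errors, power about 98%.

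So if the trial drug were counted, a significant difference would be almost certain even with identical use of other antibiotics. If it is left out, the built-in difference is 0.

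**The case against.** The strongest reply is that this is untidy drafting with no demonstrated harm. The collection rule is common to both arms. Appendix 9 defers to sections 7.5 and 7.6, so its Day 5 label may simply be a slip. Section 7.6 introduces its list as examples, and section 11.2 promises that the eCRF will capture everything the protocol requires, so a date field may exist. Clarithromycin and other antibiotics are already recorded separately, so a count without the trial drug can be derived. All these outcomes are exploratory.

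Most of that stands. It does not remove the contradiction between 3.3.3 and 7.6: a site that follows 7.6 as written returns a value over a different period from the one defined, and no date field is stated.

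A reader might go further and infer that the peaks are biased against clarithromycin because its visits will fall later. There are reasons to think of it: the trial is open-label, the Day 7 visit also records clarithromycin doses, and the safety reporting window in section 9.2 can reach day 10. But dosing ends by day 7 at the latest, which is the nominal visit day, and no passage indicates arm-dependent timing. The documents support possible bias, not bias.

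A reader might also infer that the dose outcome counts the trial drug. The protocol does not say so; it leaves the point open, and only the literal reading includes it. Counting days of therapy instead of doses would be a preference, not the correction of an error.

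**Conclusion.** The point holds as an inconsistency. The six marker outcomes are defined over 7 days but collected over 7 to 10, with a third window of 5 days for vital signs in Appendix 9. Values collected as 7.6 describes would not match the defined outcome and, unless dated, could not be brought back to it. The consequence is noise and ambiguity in both arms. Extending the window from 7 to 10 days moves the mean maximum by about 0.03 to 0.30 SD of the 7-day maximum, depending on the assumed trend and correlation. Between-arm bias would need visit timing that differs by arm, which is not shown.

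The dose outcome is under-defined. Its literal reading builds in up to 10 extra doses in the intervention arm.

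Severity is low. Only exploratory outcomes are touched; the primary outcome, sample size and error rates are unaffected.

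**What to change.** - In section 7.6, Appendix 9 and the eCRF, limit each highest or lowest value to the first 7 days after randomisation, whatever the date of the visit. Alternatively, record the date of each extreme, and where it falls after day 7 also record the most extreme value within the first 7 days.
- Replace the Day 5 label in Appendix 9 so that it agrees with section 3.3.3.
- In section 3.3.3, define the antibiotic outcome as doses of non-trial antibiotics in the first 7 days, using the item for other antibiotics that section 7.6 already collects, and give that item the same 7-day limit.

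The cost is protocol and eCRF wording and at most a few extra case-note fields per marker. No extra sampling or new analysis is needed. It is best done early, since undated values already entered would have to be abstracted again from case notes.
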